12.5 Analysis Populations

Intent to Treat Populations

An intent-to-treat analysis will be performed using all patients who were randomised and received a study device. Patients missing the measure of the primary end point (i.e. completed surgery and did not attend the 24 month visit) will be considered missing in the intent to treat analysis; no imputation of missing data will be conducted for any variables.

13.0 SELECTION CRITERIA FOR INVESTIGATORS AND CLINICAL MONITORS

- The Investigator/s selected to participate in this study is/are qualified Orthopaedic surgeon/s.
- Research assistants and study staff will be representatives of the Institute under the direction of the Principal Investigator.
- Any conflicts of interest (including financial assistance from other parties) will be declared by Investigators and research personnel before the commencement of the trial.
- Investigators must maintain a list of any delegated duties with respect to the trial, and the persons and qualifications of those persons to whom the duties are assigned.
- Sites must be able to demonstrate that adequate subject recruitment is likely to be possible, with necessary time available to conduct the study to GCP requirements, and with adequate facilities and trial staff.

- Investigators must provide medical care to a trial participant that is necessary as a result of any adverse event experienced during or following the trial that is deemed related to the trial.
- Investigators must possess, prior to trial commencement, a favorable Ethics Committee endorsement of trial protocol, Patient Information and Consent forms and any other information given to subjects.
- All trial related documents are subject to Ethics Committee review. A regular trial report is also mandatory for provision to the Ethics Committee (in accordance with local requirements).
- The Investigator/Institution shall permit trial related monitoring, audits, Ethics review and regulatory inspections, by providing direct access to source data/documents and any other trial related documentation.
- The trial **MUST** be conducted according to the approved protocol.
- Any deviation from the protocol must be documented for later review.
- No deviation from protocol may occur without Ethics Committee endorsement, unless it is required to prevent imminent harm to participants
- Investigators must ensure subjects have given informed, written consent, with all trial procedures and risks adequately explained.

14.0 ADMITTANCE OF PATIENT

The Investigator must wait for written Ethics Committee and Governance approval prior to beginning the study or enrolling participants.

A patient will be identified as a patient in this clinical trial upon signing a Patient Information Sheet and Consent form.

A review of the inclusion and exclusion criteria must be completed by the Investigator pre-operatively for each patient.

15.0 PATIENT ACCOUNTING

The Investigator or designee will complete an informed consent log with details (patient number and initials) of any patient signing a consent form to participate in this study.

Clinical trial data will be monitored regularly to identify any trends and adverse events. Documentation of participants who voluntarily withdraw from the study or who are lost to follow-up will be obtained on a Study Termination Form.

16.0 QUALITY ASSURANCE OF DATA

Case Report Forms (CRFs) or electronic Case Report Forms (eCRFs) will be routinely reviewed by the Principal Investigator for completeness and accuracy as well as any evidence which may be indicative of patient risk. When any discrepancies are noted, they will be resolved with the Investigator and/or individual designated by the Investigator. When the data are incomplete, attempts will be made to obtain the data whenever possible.

Clinical Research staff from Stryker Australia will monitor the investigational site at regular intervals to ensure compliance with the protocol and capture of any data or complications not already documented. Verification of the data from source documents will also be conducted by the Stryker monitors.

17.0 MANAGEMENT OF INTERCURRENT EVENTS

17.1 Concurrent illness/procedures

Participants requiring concurrent procedures or medications for inter-current illnesses or adverse events will not be restricted throughout the study. Given the typical patient population receiving knee joint replacements, it can reasonably be expected that concurrent illnesses or procedures may be experienced by study participants.

17.2 Withdrawal from Study

Participants will be advised that they may voluntarily withdraw from the study at anytime, for any reason and they are not obligated to reveal the reason to the Investigator and it will not affect their medical care. However, in such cases, appropriate effort will be made to determine the reason for withdrawal from the study. The Investigator may request a letter from the patient noting his or her desire to withdraw from the study. All attempts to locate participants lost to follow up will also be documented.

Participants will be informed that should they withdraw from the study they should remain under the care of an appropriately experienced physician until the physician deems further follow-up unnecessary.

The following are circumstances for which a patient would be identified as not continuing their participation in the study:

- Study Completed / Terminated
- Screen Failure
- Death
- Unable to Return
- Unwilling to Return
- Concurrent Illness
- Lost to follow-up
- Re-operation of the affected knee joint, including revision of knee replacement components
- Incorrect implant(s)/device(s) used, device not included in protocol
- Other

Additionally, the patient may be withdrawn by the Investigator, if he/she is unable to continue participation in the study due to some condition unrelated to this study.

A Study Termination Form will be completed for all participants who withdraw from the study.

<http://ssp.intranet/sites/raqa/qms/documents/FM-CRD-029.docx>

MAKORCT-15 Final version 5.0 22 February 2018

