11.0 EVALUATIONS

All data will be recorded on Case Report Forms or via Electronic Data Capture (EDC). The surgeon or study coordinator will complete and sign forms at the time of each protocol required visit.

The following data will be collected for all patients:

- **Patient Demographics:** A record of the patient's date of birth, gender, height, and weight will be obtained pre-operatively.
- **Medical History:** Relevant medical history will be recorded pre-operatively.
- **Surgical Details:** A summary of the surgical procedure will be collected during the operation. This will include details of the prosthetic components implanted, operating time and comments.
- **Patient outcome measurements:** Surgeon assessment of patient clinical outcomes will be recorded at various study visits. The following outcome scores will be recorded at time points as set out in the patient evaluation schedule. These include pre-operative, 6 week, 3 month, 12 month and 24 month follow-up visits (see Appendix 3):
 - **Oxford Knee Score (OKS):** A 12 item questionnaire was developed to measure outcomes of patients undergoing total knee replacement (Dawson et al. 1998). The score is a self-completed questionnaire that asks patients to answer questions on their pain levels and function (Whitehouse et al. 2005).
 - **EQ-5D Euro-Qol (EQ-5D-5L):** The EQ-5D-5L is a standardised patient-completed instrument for use as a measure of health outcome (Fransen and Edmonds, 1999). It consists of 5 dimensions: mobility, self care, usual activities, pain/discomfort, and anxiety/depression. There are 5 levels of severity to select from within each dimension.

- **VAS Pain:** A graphic Visual Analogue Scale (VAS) used as measurement instrument for patients to indicate their level of pain. The amount of pain that a patient feels is believed to range across a continuum from none to an extreme amount of pain i.e. from the patient's perspective this spectrum appears continuous - their pain does not take discrete jumps, as a categorization of none, mild, moderate and severe (Wewers et al. 1990).

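### Patients who stop attending leave the study and count as missing the 24-month OKS, although the score is self-completed and could be collected without a visit

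*Combined protocol and SAP*

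**What the plan says.** Protocol section 17.2 opens a list with "The following are circumstances for which a patient would be identified as not continuing their participation in the study". Among the entries are "Unable to Return", its counterpart for patients unwilling to return, and "Concurrent Illness". None carries a threshold of severity or duration. A separate sentence adds that "the patient may be withdrawn by the Investigator, if he/she is unable to continue participation in the study due to some condition", where the condition must be unrelated to the study. A Study Termination Form is completed for everyone who withdraws.

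Section 12.5 describes "Patients missing the measure of the primary end point (i.e. completed surgery and did not attend the 24 month visit" as missing in the intent-to-treat analysis, and rules out imputation for all variables.

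Section 11.0 says of the OKS: "The score is a self-completed questionnaire that asks patients to answer questions on their pain levels and function". It describes EQ-5D-5L, VAS pain and the FJS as completed or reported by the patient too. The same section has the surgeon or coordinator complete and sign the forms at each visit. The evaluation schedule in section 1.0 places the OKS at baseline, 6 weeks, 3, 12 and 24 months, and the other three scores at baseline, 3, 12 and 24 months.

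Section 12.4 analyses the primary and continuous secondary variables with a mixed model for repeated measurements (MMRM). Sections 16.0 and 21.2 say in general terms that incomplete data will be pursued where possible.

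**The concern.** Both arms receive a one-off implant, so there is no continuing study treatment to stop. Leaving the study therefore mainly means that data stop. A patient who cannot travel at month 24, or who is ill with something else, can often still answer a 12-item questionnaire about the knee. The plan does not say that such a patient will be asked, or that the answer would count if it came.

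Patients who are ill, or who do not want to come back, are unlikely to be a random sample on a score of pain and function. If the reasons for absence, or the outcomes of those absent, differ between the arms, the 24-month comparison is biased. The extra recruitment allowed in section 4.0 restores numbers but does not remove that selection.

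**Working it through.** **1. The passages side by side**

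- Section 17.2: a patient with one of these three reasons is classed as not continuing.
- Section 12.5: no attendance at 24 months means no primary endpoint.
- Section 11.0: the OKS does not need an examiner, but form completion is tied to visits.
- Sections 16.0 and 21.2: attempts will be made to obtain incomplete data. No method is named, and neither section says that a score obtained without attendance counts under section 12.5.

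No section provides for the OKS by post, telephone or electronic means, or for continuing it after a section 17.2 event.

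**2. The plan's own sample size (section 12.2)**

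Inputs: two-sided alpha 0.05, power 80%, difference 6.0, SD 8.0, so the standardised difference is 6/8 = 0.75. The two-sample t-test needs 28.9, rounded to 29 per arm, with power 0.801 at 29. Then 29 × 1.2 = 34.8, rounded to 35. Both stated figures are reproduced. The allowance is 35 − 29 = 6 losses per arm, or 6/35 = 17.1%.

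**3. Precision**

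SE of the difference = SD × √(2/n).

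- n = 29: 8 × √(2/29) = 2.10
- n = 32 (3 of 6 losses recovered, an assumption): 8 × √(2/32) = 2.00

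The SE falls by 0.10/2.10, about 5%. For scale, completers-only t-test power from 35 per arm is 0.871 with none missing, 0.834 with 10% missing and 0.787 with 20% missing.

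**4. Bias in a completers-only comparison**

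Within an arm, the completers' mean exceeds the full-arm mean by p × shortfall. Here p is the proportion lost, and the shortfall is the completers' mean minus the mean of those lost. With the same p in both arms, the treatment difference shifts by p × (between-arm difference in shortfall). The documents give neither quantity, so both are assumed over a range:

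| Losses per arm | 2 points | 4 points | 8 points |
|---|---|---|---|
| 2 of 35 | 0.11 | 0.23 | 0.46 |
| 3 of 35 | 0.17 | 0.34 | 0.69 |
| 6 of 35 | 0.34 | 0.69 | 1.37 |

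For example, 6/35 × 8 = 1.37. Against the postulated 6 points, the range is 0.11/6 = 2% to 1.37/6 = 23%. Halving the losses from 6 to 3 halves the shift.

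**The case against.** **The list may only be disposition codes.** It also contains study completion, death and an open category, and the Study Termination Form follows it. That reading is fair. But the lead-in is worded as a rule, and nothing says that questionnaires continue once a patient is recorded under one of these reasons. One sentence would settle it.

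**Section 12.5 does not forbid remote scores.** What it makes missing is the measure itself, and non-attendance is given as the explanation of that. Together with the retrieval statements in sections 16.0 and 21.2, a site could accept a posted OKS. It could equally decide that the endpoint is missing by definition. The text does not decide between them.

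**The MMRM already handles missing visits.** It does use the 6-week, 3-month and 12-month scores of a patient absent at 24 months, so the absence of imputation is not in itself a defect. This stands as a reason to expect a smaller bias than the completers-only figures. The model is valid under missing at random, which the protocol neither states nor examines in a sensitivity analysis. Absence through illness or unwillingness is where that assumption is least secure.

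**Stronger readings that the documents do not support.**

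- A reader might infer that section 17.2 contradicts section 17.1, which says "Participants requiring concurrent procedures or medications for inter-current illnesses or adverse events will not be restricted throughout the study". That sentence concerns concurrent procedures and medications. Section 17.1 describes illness as expected but does not say that it can never end follow-up, so the two sections can stand together.
- A reader might infer that an investigator who knows the arm can end data collection at will. The clause applies only to a patient unable to continue. No blinding is described and inability is not defined, but this is not open discretion.
- A reader might take 1.4 points as the expected bias. That figure needs all 6 budgeted losses to be of this kind, although section 17.2 also lists death, re-operation, incorrect device and loss to follow-up. It also needs a between-arm difference of a full SD, larger than the postulated effect, and no help from the MMRM.

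**Conclusion.** The point holds as an avoidable loss of primary-endpoint data. Followed as written, the plan may discard 24-month scores that could be obtained, from patients whose absence is probably related to health. It is neither a contradiction between sections nor an error in the sample size, which is reproduced.

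Bias matters more here than precision. The illustrative shift is about 0.1 to 1.4 points on a postulated difference of 6, and less to the extent that the MMRM recovers it. It rests on assumed losses of 2 to 6 per arm, equal in both arms, and an assumed between-arm difference in shortfall of 2 to 8 points. The gain in SE is about 5% if half of the 6 budgeted losses are recovered. The change is worth making because it costs little, not because a large bias has been shown.

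**What to change.** **Section 17.2.** Separate the end of visit attendance from the end of outcome collection. State that a patient who stops attending because of concurrent illness, or because of being unable or unwilling to return, is still asked for the OKS, EQ-5D, VAS pain and FJS. These are requested by post, telephone or electronically at each remaining time point where they are scheduled, within the visit window, unless the patient withdraws consent to further contact. Keep the investigator-withdrawal clause for patients truly unable to continue.

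**Section 12.5.** Define the primary endpoint as missing only when no 24-month OKS is obtained by any route, and record the route for each score.

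**Cost.** Protocol wording, a line in the consent form, and postage or call time for a few patients. The downside is that some scores will be completed in a different mode from those in clinic; the recorded route lets this be described. The change concerns data collection only and alters no clinical rule.

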3.0 OBJECTIVES

PRIMARY

The primary objective of this study is:

- To compare the clinical outcomes of Knee Replacement surgery using the Oxford Knee Score (OKS) at 24 months, in patients receiving Bicompartamental Knee Replacement using Restoris MCK Multicompartmental Knee System with Stryker's robotic-arm assisted surgery system Mako, to Total Knee Replacement using the Triathlon Total Knee System performed with Stryker's robotic-arm assisted surgery system Mako.

SECONDARY

The secondary objectives of this study are:

- To determine functional and clinical outcomes of Bicompartamental Knee Replacement (BKR) and Total Knee Replacement (TKR) (including pain, function and health-related quality of life) with Restoris MCK Multicompartmental Knee System and Triathlon Primary Total Knee System at 24 months via:
 - EQ-5D: The EQ-5D is a standardised instrument for use as a measure of health outcome.
 - VAS Pain: A graphical Visual Analog Scale that patients use to indicate their level of pain.
 - New Knee Society Score 2011 (KSS): A validated score assessing surgeon generated objective measures based on technical outcomes, and subjective measures based on patient satisfaction, patient expectations and functional activity of the knee (Noble et al. 2012) (Scuderi et al. 2012).
 - Forgotten Joint Score (FJS): The Forgotten Joint Score is a newly-developed twelve-item, self-reported assessment of how aware recipients

of hip and knee joint replacement are of their joint in everyday life (Behrend et al, 2011).

- To compare incidence of loosening, reoperation and revision in patients receiving Restoris MCK Multicompartmental Knee System, compared to Triathlon Total Knee System.
- To determine length of hospital stay in patients receiving Restoris MCK Multicompartmental Knee System, compared to Triathlon Total Knee System.

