12.4 Statistical Analysis

For each treatment group the demographic data will be summarised as number of observations, mean, standard deviation, minimum, median, maximum for continuous variables such as age, and as frequency and percentage for categorical variables such as gender.

For the test of the treatment effect the null hypothesis is no difference between the means of the 2 treatment groups, and will be tested against the alternative hypothesis that there is a difference between the means of the treatment groups.

The primary and continuous secondary efficacy variables will be analysed with a mixed model for repeated measurements (MMRM). The model will include factors for treatment group, time, and the interaction between treatment group, and time. For each variable the baseline values will be included in the model as covariate. The treatment effect will be tested against between patient variance. The time effect, and the interaction between treatment group and time will be tested against within patient variance. The results will be summarised as mean, and 95% CI by treatment group, and time. The least squares means will be reported for the treatment difference at each time, and overall with 95% CI. The results will be presented in tabular format, and graphically by treatment group, and time. The continuous variables of change from baseline, and percentage change from baseline will be reported as mean, and 95% CI for each treatment group.

Adverse events will be tabulated separately and reviewed for any commonalities.

The data will be summarised and comparisons presented according to:

<http://sspnet/sites/raqa/qms/documents/FM-CRD-029.docx>

MAKORCT-15 Final version 5.0 22 February 2018

- Treatment group : Restoris® MCK Multicompartmental Knee System or Triathlon Primary Total Knee System
- Adverse events: General complications, local complications, device-related complications, revisions/removals, loosening and pain.

In the event of errors in randomisation, the patient will be classified according to the treatment received. All randomisation inconsistencies will be listed.

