19.2 Reporting of Events

CONFIDENTIAL

MAKORCT-15

Any serious adverse event that occurs between patient consent and end of study, or adverse event that occurs from surgery to end of study will be recorded as such.

Additionally, any adverse event identified during radiographic review, will be recorded as such.

Adverse Events:

Any adverse event should be recorded as follows:

All information on general medical, operative and device related complications (adverse events) will be documented on Case Report Forms (CRFs) or electronic Case Report Forms (eCRFs). Information should include date of occurrence, description, severity, relationship to study device, treatment and date of resolution.

The Investigator must determine if the event is related to the device. Any adverse event in a study patient must be monitored until the event is resolved or considered non-clinically significant by the Investigator.

Expected Events: Should be reported to the Sponsor soon as possible, but not later than ten working days after the Investigator first learns of the effect.

Adverse Device Events

Should any adverse device events occur, the study staff will ensure that these are documented by the Investigator and reported immediately to the Sponsor. They should also be reported to the reviewing Ethics Committee and Institution as soon as possible, but not later than fifteen working days after the Investigator first learns of the effect, unless an earlier timeline is specified by individual study sites. The Investigator with the Sponsor will conduct an evaluation of such effects. Following this evaluation, if the Investigator determines that an unanticipated adverse device effect presents an unreasonable risk to participants, the Investigation will be terminated as soon as possible. Termination shall occur no later than five working days after the Investigator makes this determination and

<http://sspintranet/sites/raqa/qms/documents/FM-CRD-029.docx>

MAKORCT-15 Final version 5.0 22 February 2018

CONFIDENTIAL

MAKORCT-15

no later than fifteen working days after the Investigator first receives notice of the unanticipated adverse effect.

Serious Adverse Events:

Any adverse event that is considered to be of serious nature and occurs at any time point from the signing of Informed Consent Form until either the patient is terminated from the study, or 30 days post-completion, should be recorded as follows:

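### Any re-operation of the study knee ends participation, so as written these patients have no 24-month OKS, and later events in that knee may be missed

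*Combined protocol and SAP*

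**What the plan says.** Section 17.2 opens its list with "The following are circumstances for which a patient would be identified as not continuing their participation in the study". One entry is "Re-operation of the affected knee joint, including revision of knee replacement components". It makes no exception for minor procedures, and no section provides for visits, questionnaires or radiographs afterwards.

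Section 3.0 makes OKS at 24 months the primary objective. It also sets a secondary objective: "To compare incidence of loosening, reoperation and revision in patients receiving Restoris MCK Multicompartmental Knee System, compared to Triathlon Total Knee System".

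Section 12.4 analyses OKS with an MMRM containing treatment, time, their interaction and baseline. Section 12.5 defines the analysis set: "An intent-to-treat analysis will be performed using all patients who were randomised and received a study device". A patient without the 24-month measure counts as missing, and "no imputation of missing data will be conducted for any variables".

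Section 19.2 gives two recording windows. One covers "Any serious adverse event that occurs between patient consent and end of study, or adverse event that occurs from surgery to end of study". The other, for serious events, runs "until either the patient is terminated from the study, or 30 days post-completion". The end of the study is not defined.

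**The concern.** The plan stops follow-up because of an outcome that it also sets out to compare. This has two consequences.

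**Primary comparison.** A re-operated patient stays in the intent-to-treat set, and the scores before re-operation still enter the MMRM. The model then treats the absent month-24 score as if that knee had gone on like similar knees in the same arm. If re-operated knees do worse and re-operations are unequal between arms, the result moves in favour of the arm with more re-operations. Equal rates cannot be presumed, since comparing them is an objective. The plan does not say whether OKS after re-operation belongs to the comparison, and it has no sensitivity analysis for these patients.

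**Later events.** The first re-operation is recorded and followed to resolution under section 19.2, so its incidence is not lost. A revision after a lesser re-operation, or later loosening, may go unseen. The introduction (section 2.0) relies on radiographs to find loosening, and none is scheduled after termination.

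Whichever analysis is preferred, scores and films that were never collected cannot be recovered at the analysis stage.

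**Working it through.** **1. The plan's own figure.** Section 12.2 gives a difference of 6.0, SD 8.0, two-sided 0.05 and 80% power. The two-sample t-test with effect size 6/8 = 0.75 needs 28.9, so 29 per arm (power 80.1%). Then 29 × 1.20 = 34.8, so 35 per arm. The stated size reproduces.

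**2. Assumed inputs.** The documents give no re-operation rate, no OKS after re-operation and no correlation between visits. Assume k excess re-operations in one arm (1 or 3), and a month-24 deficit D of 8 to 16 points, that is, 1 to 2 SD. From the plan: 35 per arm and SD 8.0.

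**3. Decline not visible at any earlier visit.** The arm mean is too favourable by kD/35. For scale, the unadjusted standard error of the difference is 8 × √(2/35) = 1.91.

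**4. Full decline already visible at month 12.** The MMRM recovers part of the loss; what remains is one minus the regression coefficient of month 24 on month 12. Take four prior measures (baseline, 6 weeks, 3 and 12 months). Under compound symmetry with correlation 0.5 the coefficient is 0.5/(1 + 3 × 0.5) = 0.20, leaving 0.80. Under AR(1) with 0.8 it is 0.80, leaving 0.20. A simulation of the MMRM (unstructured covariance, 6000 runs; compound symmetry 0.5 and 0.7, AR(1) 0.7 and 0.8) gave 0.19 to 0.81 of kD/35. It also matched kD/35 in the no-decline case.

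| k | D | Shift, no earlier decline | Share of 6 points | In standard errors | Shift, decline seen at month 12 |
|---|---|---|---|---|---|
| 1 | 8 | 8/35 = 0.23 | 4% | 0.12 | 0.04 to 0.18 |
| 1 | 16 | 16/35 = 0.46 | 8% | 0.24 | 0.09 to 0.36 |
| 3 | 8 | 24/35 = 0.69 | 11% | 0.36 | 0.14 to 0.55 |
| 3 | 16 | 48/35 = 1.37 | 23% | 0.72 | 0.27 to 1.10 |

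In the last column the shifts are 1 to 6% of the planned difference for one excess re-operation and 2 to 18% for three.

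**5. Balanced arms.** With three re-operations in each arm and D = 16, the simulated shift was -0.01 to 0.01.

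**6. Power.** This is a minor matter. Losing 1 to 4 further patients from one arm, beyond the 29 evaluable, lowers power from 80.1% to between 79.4% and 76.9%.

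**7. The two windows in section 19.2.** If the end of the study means the end of the trial, the first window runs past termination and the second stops at it, so they conflict for terminated patients. If it means the patient's own last day, they agree for terminated patients but differ by 30 days for completers. They need reconciling on either reading.

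**The case against.** The list in section 17.2 also contains entries such as study completion and other reasons, so it can be read as disposition codes; it does not say in so many words that data collection stops. Section 5.0 promises two years of follow-up, and section 16.0 says missing data will be sought and that monitors look for undocumented complications. That stopping follows is therefore an inference. It is still the natural reading: the lead-in says participation does not continue, and a visit not scheduled after termination is not incomplete data to be chased. If the sponsor meant otherwise, sites could still apply the wording differently.

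On size, the deficits of 1 to 2 SD are assumed, and a minor re-operation might leave almost none. If the decline showed at all three earlier post-operative visits, the remaining fraction would be 0.20 to 0.40, and the largest month-12 shift, 1.10, would fall to 0.55. Conversely, a re-operation before month 12 removes the month-12 score too, so that case does not cover every patient. These points stand as limits on the illustration.

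The plan's comparison is also not strictly as randomised: section 12.5 requires receipt of a device, and section 12.4 classifies randomisation errors by treatment received. The argument here does not depend on that. Comparing scores only while the original implant is in place is a defensible target, but the plan does not declare it.

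**Conclusion.** The concern holds. As written, the plan creates missing 24-month scores for a reason tied to outcome, and possibly to arm, and handles them only under missing at random. That the text does this is clear; how much it matters in this trial is unknown. Under the assumptions above, the shift ranges from about zero with balanced re-operations to 1.37 points with three excess re-operations, a 16-point deficit and no earlier decline. One excess re-operation moves the result by at most 0.24 standard errors, so a few such patients are unlikely to decide the trial alone. The event-capture gap is narrower: it concerns later events in an already re-operated knee. The point should be fixed because the remedy is cheap and the data cannot be collected afterwards.

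**What to change.** - In section 17.2, remove re-operation and revision from the reasons for ending participation. Record them as events, and continue scheduled OKS, other questionnaires, radiographs and adverse event collection to 24 months. Voluntary withdrawal is unaffected.
- In sections 12.4 and 12.5, state that OKS collected after re-operation is included in the intent-to-treat MMRM.
- Add one sensitivity analysis that excludes scores after re-operation. This needs no imputation and shows the result for the knee as first implanted. An alternative is to assign an unfavourable month-24 value, such as the baseline OKS. That is weaker, because it overrides observed scores, and it would require amending the no-imputation sentence in section 12.5.
- In section 19.2, define the end of the study and reconcile the two recording windows.

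The cost is a protocol amendment, which section 18.0 makes subject to written Ethics Committee approval, plus the remaining visits for a few patients and one extra analysis. The sample size does not change. The drawback is that some 24-month scores will describe a re-operated or revised knee, possibly with a different implant; the sensitivity analysis shows how much that matters.
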